7 QUALITY CONTROL AND ASSURANCE

7.1 Appropriateness of Measurements

- MRI is a standard method to study the evolution of the bones, liver and spleen impairment, the only difference with the standard practice is that a second review of all document will be conducted in a central review center in order to have standardized measurement. Patients for whom MRI is contraindicated are excluded from the study.

Training will occur at an Investigator meeting or at the site initiation visit or both, and instruction manuals will be provided to aid consistency in data collection and reporting across sites.

7.2 Monitoring

Clinical sites will be monitored by the Sponsor or its designee to ensure the accuracy of data against source documents. The required data will be captured in a validated clinical data management system that is compliant with the FDA 21 CFR Part 11 Guidance and other global guidances as required. The clinical study database will include an audit trail to document any evidence of data processing or activity on each data field by each user. Users will be trained and given restricted access, based on their role(s) in the study, through a password-protected environment.

Data entered in the system will be reviewed manually for validity and completeness against the source documents by a clinical monitor from the Sponsor or its designee. If necessary, the study site will be contacted for corrections or clarifications; all missing data will be accounted for.

Serious adverse event information captured in the clinical study database will be reconciled with the information captured in the Pharmacovigilance and Risk Management database.

8 PLANNED STATISTICAL METHODS

8.1 General Considerations

Statistical plan will be written and Statistical analysis will be conducted by CenBiotech using SAS 9.3 and under the authority of [name], Public health specialist and biostatistician, head of the medical evaluation Chair of the Business school of Dijon. A detailed analysis plan will be secondary provided and validated by Shire.

8.2 Determination of Sample Size

There is no predefined sample size but in order to reflect daily practices, the study may include all patients presenting type 1 Gaucher disease and treated with VPRIV® in France.

So, based on data from the CETG, a sample size from 40 to 50 patients could be expected.

8.3 Analysis Populations

All patients included in the study will be included in the statistical analysis

8.4 Demographics and Baseline Characteristics

The socio-demographic and clinical characteristics of the cohort of patients with type 1 Gaucher's disease and the arrangements for their care are described by the usual parameters, mean and standard deviation for quantitative variables, frequencies and percentages for qualitative variables.

8.5 Primary Endpoint(s) or Assessments

The changes pre and post treatment with velaglucerase alfa of the spine and femur BMB score will be described and compared using Wilcoxon signed-rank test. The analysis will be conducted successively on all MRI assessable and on optimal quality MRI only.

Primary Safety Endpoint(s)

Adverse events will be coded using MedDRA and described as recommended in ECH procedures as far as possible due in particular to retrospective conditions..

Primary Efficacy/Effectiveness Endpoint(s)

The values observed at the different follow up times and the variations between the reference MRI and the follow-up MRI, of the BMB weighted score at T1 and T2 measured at the femur and lumbar spine, are described by mean and standard deviation and the 95% confidence interval will be calculated. These values will be compared at the different follow up times with test on repeated data: ANOVA on repeated series or Wilcoxon rank test, depending on the nature and distributions of the studied variables.

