3 STUDY ENDPOINT

3.1 Primary Endpoint(s)

The primary endpoint is the change over time between the baseline MRI and the follow-up MRIs, of the BMB score (11) weighted at T1 and T2 and measured at the femur and lumbar spine .

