4 STUDY PLAN

4.1 Data collection and transmission

All data entered will be used for analysis purposes and results will be submitted to inform regulatory agencies. Patient care and management is freely determined by the participating physician, in the framework of an observational study reflecting the daily medical practice. The clinical data, the results of routine clinical and laboratory testing that are part of standard medical care for patients with Gaucher disease will be collected from the medical record of the patient :

- Socio-demographic characteristics
- History of the disease and context of diagnosis
- Medical background
- MRI: abdominal and bone, as defined below
- Clinical data available in the range from 3 months before or after each MRI
- Biological data available in the range from 3 months before or after each MRI
- Treatment with VPRIV® (velaglucerase alfa), including the doses and regimens

4.2 The MRI images collected during the study:

The MRIs performed in the patient's usual medical follow-up for its Gaucher disease (abdominal MRI (liver and spleen) and bone MRI (back injury pelvis, lower limbs) and / or whole-body MRI) will be collected. Among the MRIs available in the patient's medical records, MRIs will be collected the following:

- Reference MRI: MRI closest to the date of initiation of VPRIV® in the five years preceding the start of treatment or within three months after initiation of VPRIV®.
- MRIs of the retrospective phase of the study: All MRIs available between the reference MRI and the inclusion date of the patient.
- MRIs of the prospective phase of the study: all the MRIs that will be realized during the prospective phase of the study, that is to say, during the year following the date patient inclusion in the study.

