4.12 Study Duration

The study is developed in conjunction with the French Referral Centers of Lysosomal Diseases, and the French Gaucher Treatment and Evaluation Committee (CETG: Comité d'Evaluation du Traitement de la maladie de Gaucher). It is a retro prospective observational study of the French cohort of patients with type 1 Gaucher disease treated with VPRIV® in everyday clinical practice.

It consists of two phases: a retrospective and a prospective phase with a 1 year inclusion period.

Phase I: retrospective phase

The retrospective period includes the period between the date of the baseline MRI to the patient's date of inclusion in the study. The reference MRI is defined as the closest MRI to the initiation of VPRIV®, within the past five years, or within three months after initiation of VPRIV®.

Phase II: prospective phase

Prospective period will be one year from the date of patient inclusion in the study.

The final MRI

MRI being performed in current practice every 2 years, the final MRI follow-up performed corresponds to those in the previous year or in the year following the patient's inclusion.

The duration of the study will be 2 years: a 1-year inclusion period to be sure to include all patients treated with VPRIV® (reviewed annually in consultation each year) and a prospective follow-up period of 1 year. Provisional timetable for the study:

CCTIRS / CNIL authorization	October 23, 2015
Inclusion of the first patient in the study	September 30, 2016
Inclusion of the last patient in the study	September 30, 2017
Last visit of the last patient	September 30, 2018
Study clinical report	January 31, 2019

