5.1 Inclusion Criteria

1. Patients of any age or gender with confirmed diagnosis of type 1 Gaucher disease,
2. Patients treated with VPRIV® at the beginning of the study. Prior starting VPRIV® patients could be either treatment naïve or previously treated with any other Gaucher treatment than VPRIV®.
3. Patients should have one MRI data in the 5 previous years before starting VPRIV® treatment
4. Informed written consent obtained from the patient, and/or patient's parent(s), and/or legal representative. Assent, if old enough to grant, will be obtained from all patients under the age of 18 years.

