8.6 Secondary Endpoint(s)

The socio-demographic characteristics of the patients, the history of their disease, the context of the diagnosis, the medical history, the clinical evaluation criteria of liver and spleen, the MRI evaluation criteria of the liver and spleen, the MRI evaluation criteria of bone lesions and the biological evaluation criteria are described by mean and standard deviation for quantitative variables, by frequency and percentage for categorical and ordinal variables. The 95% confidence intervals will be calculated. The evolutions of these criteria at the different periods when they are collected are described by mean and standard deviation or percentage changes. They are compared between the different times of the study by test on repeated data: ANOVA on repeated series or Wilcoxon rank test, depending on the nature and distributions of the studied variables

The analysis will describe and analyze the evolution of bone disease on the basis of the MRI's measures. It will describe and analyzes also the evolution of patients on the basis of their other MRI measures, clinical and laboratory data. It will describe also the incidence of spleen infarcts, fibrosis, liver nodules and their evolution under treatment by velaglucerase alfa.

Comparisons shall be made by analysis of variance on repeated series for quantitative variables or by Wilcoxon signed rank tests if normality is not demonstrated and by McNemar tests or rank tests on repeated series for quantitative or ordinal criteria

Changes over time in hepatomegaly, presence of lithiasis, nodules or infarct will be analysed using macNemar test and changes in liver measurements will be compare using analysis of variance on repeated series,

Changes over time in splenomegaly, presence of nodules or infarct will be analysed using Mac Nemar test and changes in spleen measurements will be compare using analysis of variance on repeated series,

Change in marrow infiltration, bone infarction, osteonecrosis, pathological fractures vertebral will be analysed using Mac Nemar test or Wilcoxon rank test.

Changes in fatigue, abdominal pain, bone pain: hemorrhagic syndrome, lung disease and neurological disease will be analysed using Mac Nemar test or wilcoxon rank test

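### The BMB change that section 8.5 presents as pre and post velaglucerase alfa starts at an MRI up to five years before the drug, so it can include change that arose off the drug, in an unknown direction

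*Protocol*

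**What the plan says.** Section 4.2 of the protocol fixes the starting scan, with the three months counted forward from VPRIV start: "Reference MRI: MRI closest to the date of initiation of VPRIV® in the five years preceding the start of treatment or within three months". Sections 4.9 and 4.12 repeat this definition. The entry rule has the same five-year reach: "Patients should have one MRI data in the 5 previous years before starting VPRIV® treatment" (section 5.1). No shorter limit appears anywhere.

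The primary endpoint is "the change over time between the baseline MRI and the follow-up MRIs" (section 3.1). The effectiveness paragraph of section 8.5 accordingly describes "the variations between the reference MRI and the follow-up MRI". The opening sentence of section 8.5 gives the comparison another name: "The changes pre and post treatment with velaglucerase alfa of the spine and femur BMB score will be described and compared", by Wilcoxon signed-rank test.

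Before VPRIV, patients may be treatment-naive or have received any other Gaucher treatment (section 5.1). All included patients are analysed (section 8.3). The only repeat analysis attached to the primary comparison concerns image quality (section 8.5).

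For lesions, section 8.6 will describe the "incidence of spleen infarcts, fibrosis, liver nodules and their evolution under treatment by velaglucerase alfa". On scan frequency, section 4.12 says "MRI being performed in current practice every 2 years".

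**The concern.** The name and the quantity differ. A change that starts at the reference MRI covers two stretches of time: from that scan to VPRIV start, and from VPRIV start to the follow-up scan. Only the second is on VPRIV. In a previously treated patient the first stretch may have been spent on another drug; in a naive patient it is untreated disease. Nothing in section 8 separates the two, and no MRI is tied to the date of initiation, although section 6.6 does record clinical and biological status at that date.

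This matters because of the intended use. Section 1.3 offers the data as help in judging what the treatment does to these parameters and as a partial answer to a health authority's request. Section 4.1 says the results will go to regulatory agencies. A reader given a significance test on a pre and post comparison will take the whole change as belonging to VPRIV.

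**Working it through.** The protocol has no figure to reproduce: section 8.2 sets no sample size and only expects 40 to 50 patients. The steps below size the issue. Let g be the years from reference MRI to VPRIV start and T the years on VPRIV at the follow-up MRI. The protocol does not state T, so a range is assumed.

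**1. Share of the measured interval that is before VPRIV**, g/(g+T), for T = 5 and T = 2:

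- g = 1: 1/6 = 17% and 1/3 = 33%
- g = 2: 2/7 = 29% and 2/4 = 50%
- g = 5 (permitted limit): 5/10 = 50% and 5/7 = 71%

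These are shares of time, not of effect.

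**2. How large g is likely to be.** Take scans every two years (section 4.12) and assume their timing is independent of VPRIV start. The last scan before start is then uniformly 0 to 2 years old. If the next scan falls within three months after start, it is the closer one and becomes the reference.

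- Probability that the reference is after start: 0.25/2 = 12.5%, with mean gap −0.125 year.
- Otherwise (87.5%) the gap is uniform on 0 to 1.75 years, with mean 0.875.
- Overall mean: 0.875 × 0.875 − 0.125 × 0.125 = 0.75 year.
- Gap over one year: (1.75 − 1)/2 = 37.5% of patients.
- Share of the interval at the mean gap: 0.75/5.75 = 13% for T = 5; 0.75/2.75 = 27% for T = 2.

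**3. What the gap could do to the test.** Suppose there is no change at all on VPRIV and a net drift of d standard deviations before it. With two-sided alpha 0.05 (assumed) and a normal approximation, a paired test is significant with probability Φ(d√n − 1.96) + Φ(−d√n − 1.96). For n = 40 to 50:

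- d = 0.2: 24 to 29%
- d = 0.3: 47 to 56% (46 to 55% with the Wilcoxon efficiency factor 3/π)
- d = 0.5: 88 to 94%

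The protocol gives no value for d, so these figures are only illustrations.

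**4. Lesions.** At a constant rate λ, the share of new lesions that arose before VPRIV is (1 − e^(−λg))/(1 − e^(−λ(g+T))). With λ = 0.05 per year (assumed; range 0.02 to 0.10) and T = 2, the share is 35% (34 to 37%) for g = 1 and 52% (51 to 55%) for g = 2.

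**The case against.** The strongest reply is that sections 3.1 and 8.5 already define the right quantity, change from the reference MRI, and that the objective in section 2.1 is descriptive. On this view only one loose label is at fault. It is true that the computation is stated correctly. But the label stands in the sentence that names the primary comparison and its test, and sections 1.3 and 4.1 show that the result is meant to bear on the effect of treatment.

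Second, change on VPRIV is not hidden. The reference is the closest scan, so every later scan falls after VPRIV start and only the first interval can contain the gap. A patient with two or more later scans contributes an interval wholly after VPRIV start. This stands and is used in the fix. It does not help patients with a single follow-up MRI.

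Third, section 8.1 promises a detailed analysis plan, which is not at hand and may handle the gap. That is fair for the supporting analyses. The reference window and the pre and post label, however, are protocol text.

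Three stronger readings are tempting, and the documents support none of them. A reader might infer that VPRIV is systematically flattered. The protocol gives no figure for change before VPRIV: improvement on an earlier drug would count for VPRIV, untreated worsening would count against it, and a reference scan up to three months after start misses early on-drug change. A reader might take five years as typical; it is the limit, and two-yearly practice implies far shorter gaps. A reader might also conclude that section 8.6 overstates lesions arising under VPRIV. There, the reference to treatment most naturally attaches to the evolution of the lesions, and no section says that new lesions are counted as arising on the drug.

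**Conclusion.** The point holds for the primary BMB change. The plan applies a pre and post VPRIV label to a change that can include untreated or otherwise-treated time, and nothing in section 8 identifies that part. The direction of the resulting error is unknown, and in a pooled mean errors of opposite sign may partly cancel. The typical size is moderate: 13 to 27% of the interval at the mean gap, with more than a third of patients over one year. This rests on two-yearly scans timed independently of VPRIV start and on an assumed 5 to 2 years on VPRIV. Individual patients at the permitted limit could reach 50 to 71%. For lesions, the text of section 8.6 is unclear rather than wrong, and only a clarification is needed.

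**What to change.** Keep the five-year entry window and the all-patient analysis.

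- **Section 8.5, wording:** name the all-patient result as change in spine and femur BMB score since the reference MRI, and drop the pre and post label.
- **Section 8.5, table:** show the distribution of the gap between reference MRI and VPRIV start, with the treatment received during it (none or another Gaucher treatment).
- **Section 8.5, supporting results:** (a) the same change in patients whose reference MRI is close to VPRIV start, for example within 12 months; (b) where two or more MRIs on VPRIV exist, the change between them, reported as wholly on-VPRIV change.
- **Section 8.6:** describe a lesion that is absent on a pre-VPRIV reference MRI and first seen on the next MRI as arisen since the reference MRI, not as arisen under VPRIV.

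A 24-month limit would not serve for (a): with two-yearly scans it would exclude almost nobody. Under the model in step 2, a 12-month limit keeps 12.5% + 50% = 62.5% of patients, which is 25 of 40 or 31 of 50. Their mean gap is (0.5 × 0.5 − 0.125 × 0.125)/0.625 = 0.375 year, so the pre-VPRIV share falls to 0.375/5.375 = 7% for T = 5 and 0.375/2.375 = 16% for T = 2. The gap is reduced but not removed.

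The cost is wording, one table and two supporting results. The scan and start dates are already needed to identify the reference MRI. Treatment status at the baseline MRI is already needed for the comparison in section 2.2, but section 4.1 lists only VPRIV treatment among the data collected, so dates of earlier Gaucher treatment may need a case report form field. The downside is smaller numbers in the supporting results.

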Copies of MRIs and coded will be sent securely at BioClinica center for analysis. In case of connection failure from the participating centers, MRI scans will be sent by post.

Data from this second reading by BioClinica will be retrieved for analysis. The results of the second reading by BioClinica will be forwarded to investigation center, which will include them in the patient's record.

Statistical analysis

Primary endpoint:

The values observed at the different follow up times and the variations between the reference MRI and the follow-up MRI, of the BMB weighted score at T1 and T2 measured at the femur and lumbar spine, are described by mean and standard deviation and the 95% confidence interval will be calculated. These values will be compared at the different follow up times by test on repeated data: ANOVA on repeated series or Wilcoxon rank test, depending on the nature and distributions of the studied variables.

Secondary endpoints:

Socio-demographic characteristics of the patients, history of their disease, context of diagnosis, medical history, clinical evaluation criteria of liver and spleen, MRI evaluation criteria of the liver and spleen, MRI evaluation criteria of bone lesions and the biological evaluation criteria are described by mean and standard deviation for quantitative variables, by frequency and percentage for categorical and ordinal variables. The 95% confidence intervals will be calculated. The evolutions of these criteria at the different periods when they are collected will be described by mean and standard deviation or percentage changes. They will be compared between the different times of the study by test on repeated data: ANOVA on repeated series or Wilcoxon rank test, depending on the nature and distributions of the studied variables.

Software

Data will be entered on CLINSIGHT and analysed with SAS 9.3.

Indirectly personal character of data

The patient information is sent to the radiological analysis centre in an indirectly personal form comparable to that used in therapeutic trials, namely the patient's initials and a file number. Only the practitioner at the Gaucher Disease Reference Centre knows the correspondence between this number attributed to the patient and the patient's identity.

Justification of indirectly personal character

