4.9 Overall Study Design and Plan

Figure 1. Overview of the Study Design

	0. Eligible patients (n= 40-50)	
	1. Patient inclusion (Written informed consent obtained)	
Retrospective data collection	
2. Retrospective data collection
 
The closest MRI conducted during the 5 years before the initiation of VPRIV® treatment or in the 3 months after the VPRIV® initiation is collected and corresponds to the reference MRI.
 
Clinical and biological data available 3 months before or after the reference MRI are collected
 
Medical history and clinical and biological data available, when VPRIV® treatment is initiated, are collected
 
Each MRI available since VPRIV® treatment initiation and patients inclusion is collected as well as clinical and biological data available 3 months before or after it
 
.....
 
MRI collected are anonymously sent to a central lab reading: MRI results data collection
	
Medical history
 
Clinical data
 
Laboratory data
 
VPRIV® treatment
 
MRI
 
..... VPRIV treatment
 
Centralized MRI reading:
 
 - Liver and spleen volumes - BMB score of the spine and femur
Prospective data collection	
3. Prospective follow-up:
 
For each MRI that will be conducted from the patient inclusion until the end of the one year follow up study, clinical and laboratory data available within the 3 months before the MRI and the 3 months after MRI are collected.
 
.....
 
.....
 
MRI collected are anonymously sent to a central lab reading: MRI results data collection
	
Clinical data
 
Laboratory data
 
VPRIV® treatment
 
MRI
 
.....
 
Centralized MRI reading:
 
 - Liver and spleen volumes - BMB score of the spine and femur
	
The study will last for one year from the date of the patient inclusion
 
The study is constituted of 2 phases: a retrospective and a prospective period
 
Phase I: Retrospective period
 
The retrospective period includes the period before VPRIV® treatment initiation until the beginning of this study..
 
Phase II: Prospective period
 
The prospective period will last for one year from the date of the patients inclusion
	

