6.7 Efficacy and Effectiveness Assessments

For the closest MRI realized before the initiation of VPRIV® treatment and for each MRI which will be conducted during the prospective one year period, the following information will be recorded whenever they are available in patient's dossiers. Clinical and biological status will also be recorded when treatment was started and the patient included in the study.

- Spine and femur BMB score of T1 and T2 weighted,
- Marrow infiltration, bone infarction, osteonecrosis, pathological fractures (vertebral)

The clinical status:

***Retrospective and prospective observational study of MRI changes in bone and visceral lesions of patients with type 1
Gaucher disease treated with VPRIV® (velaglucerase alfa)***

- Height, weight
- Asthenia (absent / present : mild , moderate or severe), abdominal pain (absent / present : mild , moderate or severe), chronic pain in bone (absent / present : mild , moderate or severe), hemorrhagic syndrome (epistaxis, gingival bleeding, bruising, other rated : absent / present : mild , moderate or severe), lung disease, neurological disease

The biological status:

hemoglobin (g/dl); leukocytes (cells/mm³); platelets (mm³); ACE (angiotensin converting enzyme (U/l); ferritin (mg/l); chitotriosidase (nmol / h / ml); CCL18 (ng/ml), vitamin D (nmol/l), vitamin B12 (pmol/l); SGOT/AST (U/l), SGPT/ALT (U/l), GGT (U/l), alkaline phosphatase (U/l), triglycerides (mmol / l), total cholesterol (mmol/l) gamma globulin (g/l) serum calcium (mmol/l) presence or absence of a monoclonal peak and type if any.

The review will be done on the MRI that the treating physician has addressed for a central review radiological center via the CETG after blinding of the documents.

As previously, the quality of the MRI is evaluated and classified in three categories: Optimal, sub optimal and not assessable according the following definition:

- Optimal: Sufficient anatomical coverage, good image quality with no to minimal image artifacts and compliance with the imaging protocol
- Suboptimal: Sufficient anatomical coverage, presence of moderate image artifacts and/or minor deviations to the imaging protocol, with minimal impact on the analysis
- Not assessable: Insufficient anatomical coverage and/or presence of strong image artifacts and/or severe deviations to the imaging protocol, which would lead to an unreliable analysis.

Spleen/Liver:

TEST	DESCRIPTION	FORMAT/VALUES

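### The across-time test planned for the primary BMB score assumes common follow-up times that routine-care MRIs do not have; 6.7 and 8.6 also need aligning

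*Protocol*

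**What the plan says.** Section 8.5 carries two BMB comparisons. The first is a pre/post test: "changes pre and post treatment with velaglucerase alfa of the spine and femur BMB score will be described and compared using Wilcoxon signed-rank test", run on all assessable MRIs and then on optimal-quality ones. The second, under the efficacy subheading, is "These values will be compared at the different follow up times with test on repeated data: ANOVA on repeated series or Wilcoxon rank test", the choice depending on the nature and distribution of the variable. The synopsis gives only the second: "These values will be compared at the different follow up times by test on repeated data: ANOVA on repeated series or Wilcoxon rank test". Section 3.1 defines the endpoint as change from the baseline MRI to the follow-up MRIs, in the plural.

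On which MRIs exist, 4.2 collects three sets:
- a reference MRI, the one closest to VPRIV start "in the five years preceding the start of treatment or within three months after initiation of VPRIV";
- for the retrospective phase, "All MRIs available between the reference MRI and the inclusion date of the patient";
- every MRI in the year after inclusion.

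Section 4.9 agrees: "Each MRI available since VPRIV® treatment initiation and patients inclusion is collected as well as clinical and biological data". Section 4.12 says that MRIs are done in practice "every 2 years, the final MRI follow-up performed corresponds to those in the previous year or in the year following" the patient's inclusion. Section 4.3 has the collected MRIs read centrally, BMB included, and 4.4 retrieves those readings for analysis outside the case report form.

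Section 6.7 is narrower. It lists BMB among the items recorded for the "closest MRI realized before the initiation of VPRIV® treatment and for each MRI which will be conducted during the prospective one year period".

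Section 3.2 defines the monoclonal peak as present or absent, with its type. Section 8.6 puts it in the list of laboratory parameters to be analysed by repeated-series analysis of variance.

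**The concern.** A repeated-series ANOVA needs the same occasions in every patient, and the plan has no such occasions. Physicians decide when to scan, the reference MRI sits in a window 5.25 years wide, and time on VPRIV at inclusion differs by patient. If occasions are simply numbered, each point of the described time course mixes early and late treatment, and patients with few MRIs fall out. The alternative on offer does not help, because a signed-rank test handles two paired occasions, not a series. The choice between the two is tied to the distribution of the variable, whereas the difficulty lies in the timing of the scans.

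The study is descriptive and no decision hangs on a p-value. The described course of BMB on treatment is nevertheless its main product, and the results are meant to inform regulatory agencies.

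Two smaller problems concern the same analyses. Sections 6.7 and 4.2 disagree on which MRIs carry a BMB value, and 8.6 assigns a method for continuous data to a binary finding.

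**Working it through.** The protocol calculates no sample size, power or alpha. The 40 to 50 patients in 8.2 are an expected count, so there is no planned figure to reproduce.

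**Inputs from the protocol.** MRI about every 2 years (4.12); reference window from 5 years before to 0.25 years after VPRIV start (4.2); final-MRI window 1 year either side of inclusion (4.12); prospective period 1 year; 40 to 50 patients (8.2). **Assumed, because not given:** time on VPRIV at inclusion, and the spread of MRI intervals.

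**1. Are there common occasions?** MRI dates were simulated with 2-year intervals (SD 0.25 y), for three assumed ranges of time on VPRIV at inclusion. Number of follow-up MRIs per patient:

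| Time on VPRIV at inclusion | 0 | 1 | 2 | 3 | 4 |
|---|---|---|---|---|---|
| 1–3 y | 2% | 58% | 39% | 0% | – |
| 1–6 y | 1% | 24% | 39% | 32% | 4% |
| 3–6 y | – | 1% | 40% | 53% | 6% |

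A complete-case ANOVA with two follow-up occasions would lose 2 + 58 = 60%, 1 + 24 = 25%, or 1% of patients. With three occasions, the middle row loses 1 + 24 + 39 = 64%. The first follow-up MRI falls at about 0.35 to 2.3 years on VPRIV (5th to 95th percentile) in all three rows. The size of the loss depends on the assumption; the misalignment in time does not.

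**2. Who has a final MRI as 4.12 defines it?** If MRI dates are unrelated to inclusion, the chance of at least one MRI in a window of width w is E[min(w, interval)] / E[interval].
- Intervals normal with mean 2 y, w = 2 y: (2 − SD × 0.399) / 2. SD 0.3 gives (2 − 0.12) / 2 = 94%; SD 0.6 gives (2 − 0.24) / 2 = 88%.
- Simulation that also requires the MRI to follow the reference MRI: 86–94%. So about 6–14% of patients have no final MRI in the window, that is 0.06 × 40 ≈ 2 up to 0.14 × 50 = 7 patients.

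**3. What if 6.7 alone decided which MRIs have BMB?** With w = 1 y: 1/2 = 50%, so 20 of 40 or 25 of 50 patients would have no follow-up BMB. The share with a follow-up value would be 100% for yearly MRIs, 67% for an interval of 1.5 years and 33% for 3 years. If MRI timing is also unrelated to VPRIV start, 0.25 / 2 = 12.5% (5 to 6 patients) have a reference MRI after start, which 4.2 allows and 6.7 leaves out. With 2-yearly MRIs these patients also have an earlier scan, so 6.7 would change their baseline and not remove it.

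**4. Does 6.7 decide?** Sections 4.2 and 4.9 collect every MRI, 4.3 has the collected MRIs read for BMB, and 4.4 retrieves those readings separately. Section 6.6 carries the full BMB reading table for the retrospective part, though it speaks of a single MRI. Section 6.7 concerns items available in the patient's file, while 4.3 says that BMB is not initially there. Section 6.7 is the outlier.

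**5. Monoclonal peak.** Binary in 3.2, analysis of variance in 8.6. The same section uses McNemar for lithiasis, nodules and infarct.

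**6. Does the proposed model work at this size?** In 200 simulated studies of 45 patients per scenario (interval SD 0.4 y), all fits converged. On average 40 patients gave a reference-to-final pair and 43 entered the model. With an invented plateau course of −0.46 at 6 months, a straight line in time gave −0.73 or −0.70 (with or without drift before VPRIV); a 3-knot spline gave −0.55 or −0.52. The trajectories are made up; they show only why curvature should be allowed.

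**The case against.** The strongest reply is that this is detail for the analysis plan, which 8.1 promises. Visit windows and the handling of unequal numbers of MRIs do commonly belong there, and their absence is not the point. What stands against the reply is that the protocol already names methods that presuppose matched occasions, so the analysis plan would have to depart from 8.5 to do better.

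A reader might infer from 6.7 that half the cohort will have no follow-up BMB. The documents do not support that: 4.2 to 4.4 and 4.9 have every collected MRI read centrally, so 20 to 25 patients is a worst case that arises only if 6.7 governed.

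A reader might also treat the absence of the pre/post test from the synopsis as a separate contradiction. The synopsis does describe change from the reference MRI and names a Wilcoxon test. It abridges 8.5 and should be aligned with it.

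Nor is it right that patients have no MRI in common. The reference and final MRI are defined for everyone; what is missing is a common time on treatment.

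Two objections to the remedy have force. A single final MRI would not by itself cover the 3.1 endpoint, so the time-course model is needed beside it. A signed-rank test ranks the sizes of differences, so it treats steps of an ordinal score as comparable; it is kept because it is the protocol's own choice.

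**Conclusion.** The point holds for three defects:
- The across-time comparison in 8.5 and the synopsis does not fit MRIs taken at unaligned times on VPRIV.
- Section 6.7 lists BMB for fewer MRIs than 4.2 to 4.4 and 4.9 collect and read.
- Section 8.6 analyses a binary finding by analysis of variance.

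The first matters most. The share of patients lost from a two-follow-up ANOVA runs from about 1% to 60% across the assumed ranges of time on VPRIV, and the first follow-up MRI spreads over roughly two years of treatment in each of them. These sizes rest on 2-yearly MRIs and on treatment durations that the protocol does not state. The second is an inconsistency of wording, not a demonstrated loss of data. The third concerns one secondary variable. The corrections should be made, but nothing here threatens the feasibility of the study.

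**What to change.** - **8.5 and synopsis, pre/post test.** Specify reference MRI versus final MRI as defined in 4.12 (the later one if two fall in the window), by signed-rank test, for spine and femur separately, on all assessable MRIs and then on optimal-quality MRIs.
- **8.5 and synopsis, time course.** Replace the ANOVA across follow-up times with a mixed model for change from reference, using all assessable follow-up MRIs. Include actual time on VPRIV with curvature allowed (a 3-knot restricted cubic spline is one option), the gap from reference MRI to VPRIV start (zero if the reference follows start) and a patient random intercept. Report it as a descriptive time course with 95% confidence intervals. This keeps the 3.1 endpoint covered.
- **6.7.** Align with 4.2 and 4.3, so that BMB is recorded for every collected MRI, including a reference MRI up to 3 months after start and a final MRI in the year before inclusion.
- **8.6.** Analyse presence of a monoclonal peak by McNemar, reference versus final MRI.

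Cost: rewording of 6.7, 8.5, 8.6 and the synopsis. No MRI or read is added, since the central reader already reads all collected MRIs.

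Downsides: the reference-to-final interval still varies between patients (5th to 95th percentile spread about 2.7–3.0 years in simulation), and some have no final MRI in the window, so both should be reported. The model makes distributional assumptions for a bounded ordinal score in 40 to 50 patients, which is why it should stay descriptive.
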